TRANEXAMIC ACID FOR cSDH-

A PILOT STUDY ON THE SAFETY OF TRANEXAMIC ACID FOR THE CHRONIC SUDURAL HEMATOMA POPULATION

NCT02618382

Tranexamic acid for cSDH – A Pilot Study on the Safety of Tranexamic Acid for the Chronic Subdural Hematoma Population

Study Objectives

1. Establish the safety of using tranexamic acid in the treatment of chronic subdural hematomas
2. Determine if the use of oral tranexamic acid reduces the rate of ipsilateral recurrence following drainage of chronic subdural hematomas

Background

Chronic subdural hematomas are a common problem faced by neurosurgery with an annual incidence of 13.5/100,000 persons per year and up to 58/100,000 in the over 65 years old population (Kudo). Their treatment is often complicated by recurrence with rates reported as high as 33% (Muzii). Currently there is no good strategy to help avoid this problem, which adds significantly to patient morbidity. The pathogenesis of this problem is believed to be related to the propensity of the associated neo-membranes to bleed (Ito, Weir, Lim, Labadie). Ito et.al. showed with labeled red blood cells that bleeding continues to occur into the hematoma cavity (1976). It has also been shown that there are high levels of tissue plasminogen activator in the outer membrane of chronic subdural hematomas (Ito 78 and Labadie 74). Lim et.al. found that ratio of tissue plasminogen activator to plasminogen activator inhibitor contributed to the pathogenesis (Lim 95). It has also been shown that chronic subdural hematomas have high levels of fibrin degradation products which in addition to marking the breakdown of fibrin are themselves anti-hemostatic by enhancing tissue plasminogen activator activity (Nieuwenhuizen 83), having an anti-thrombin affect (fletcher 62) and inhibiting platelet aggregation (kowalski 64) and fibrin polymerization (Alkjaersig 62). Essentially, a scenario of ongoing hemorrhage and repeated clot formation and hyperfibrinolysis leads to the expansion and recurrence of chronic subdural hematomas.

Given the importance of plasmin and hyperfibrinolysis in the pathophysiology of chronic subdural hematomas, interrupting its action and the vicious cycle it propagates seems an ideal therapeutic target. Tranexamic acid is a synthetic lysine amino acid derivative. It binds to the fibrin binding sites on plasmin or plasminogen and prevents its interaction and degradation of fibrin. This effect on the neo-membranes of chronic subdural hematomas should prevent rebleeding and the re-accumulation of the subdural hematoma.

Supporting Data

Kageyama et.al. showed the safety and potential efficacy of treating chronic subdural hematomas in their retrospective study of 21 patients. There were no recurrences in their 21 patients. Vujkovac et.al. also showed that tranexamic acid could be used safely and effectively in their case report of a hemodialysis patient who begun therapy following another recurrence after the third operation. The hematoma completely resolved and the patient made a complete recovery.

Tranexamic acid has been shown to be safe and effective in reducing blood loss and transfusions in a number of types of surgery, reduced mortality and need for urgent surgery in patients with GI bleeding and reduced bleeding associated with menorrhagia and pregnancy. Adverse effects are generally mild. Thought there is a theoretical increased risk of thromboembolic complications, multiple randomized controlled trials have not shown an increased risk (McCormack, Dunn, Katsaros, Barer, Benon). Furthermore, in a study of over 3000 gynecologic patients using tranexamic acid, Bekassy et.al. had no thromboembolic complications. This is likely because tranexamic acid has been shown to not have an effect on plasminogen in the vein wall (Astedt).

Tranexamic acid for cSDH – A Pilot Study on the Safety of Tranexamic Acid for the Chronic Subdural Hematoma Population

Study Design

This study is a single center single armed study of 50 patients to determine the safety of tranexamic acid in the chronic subdural hematoma population following surgical drainage of chronic subdural hematomas. This will be compared to historical controls. This study intends to be a prerequisite to a large nationally funded randomized control trial.

Selection and Enrollment of subjects

Inclusion Criteria:

- all patients undergoing intervention for cSDH including drainage
- cSDH will be defined as hematoma on CT imaging that is predominantly isodense to hypodense to brain
- 18-85 years of age

Exclusion Criteria

- cSDH not requiring surgical drainage
- patients undergoing bedside twist drill craniostomy
- medically unstable for surgery
- patients requiring long-term anticoagulation- unable to stay off for less than 30 days
- patients not expected to survive to the completion of follow-up
- patients comatose prior to the initiation of treatment
- history of thromboembolic problem including stroke, MI, DVT, PE
- pregnant
- minor
- allergy/sensitivity to tranexamic acid
- irreversible coagulopathy
- known clotting disorder
- bilateral hematomas with both requiring drainage
- incarcerated
- any patient not judged suitable for the study by the investigators
- women who are taking combination oral contraceptive

Study Enrollment

Patients meeting all of the inclusion and exclusion criteria will undergo standard treatment of their chronic subdural hematoma including operative treatment with the addition of preoperative and postoperative oral tranexamic acid treatment. Patients will receive a dose of 1300mg orally three to four hours prior to surgery. They will then take 1300mg orally three times daily for three days or until discharge, whichever occurs first. Tracking and follow-up will be explained to the patients and arranged by the study coordinator.

Tranexamic acid for cSDH – A Pilot Study on the Safety of Tranexamic Acid for the Chronic Subdural Hematoma Population

Study Interventions

All patients will undergo an intervention for the drainage of their subdural hematoma. The type of procedure i.e. burr-hole drainage or craniotomy excluding twist drill craniostomy will be at the discretion of the treating physician

All patients will be followed daily during their hospitalization

All patients will have follow-up CTs on postop days 1, 3, 7 and 30 +/- 7 days

All patients will have clinical follow-up on Day 30 +/- 7 days

All patients will be treated using standard ICU protocols

- neurologic status will be assessed at least every four hours for the first 48 hours
- care will be directed toward the goal of normotension and adequate oxygenation

All patients will have DVT prophylaxis with spontaneous compression devices. Pharmacologic prophylaxis will be at the discretion of the treating physician.

Experimental Interventions

Patients will receive tranexamic acid in the following dosing regimen:

1. 1300 mg times one immediately prior to surgery
2. 1300 mg orally three times daily for three days or until discharge- whichever comes first.
-First postop dosing will start 8 hours after preop dose is given.

All patients will have creatinine monitored daily while on study drug. Patients with creatinine > 1.4 will have dosage adjustments as follows:

Table 1. Dosage of LYSTEADA in Patients with Renal Impairment

LYSTEADA		
Serum Creatinine (mg/dL)	Adjusted Dose	Total Daily Dose
Cr above 1.4 and \leq 2.8	1300 mg (two 650 mg tablets) two times a day for a maximum of 5 days during menstruation	2600 mg
Cr above 2.8 and \leq 5.7	1300 mg (two 650 mg tablets) once a day for a maximum of 5 days during menstruation	1300 mg
Cr above 5.7	650 mg (one 650 mg tablet) once a day for a maximum of 5 days during menstruation	650 mg

Prohibited Interventions

Therapeutic anticoagulation

Tranexamic acid for cSDH – A Pilot Study on the Safety of Tranexamic Acid for the Chronic Subdural Hematoma Population

Clinical and Laboratory Evaluations

Presentation Day 0- CT scan, NIH stroke scale, pregnancy test, informed consent, modified Rankin Score (mRS)

Postop-
Day 1 CT Scan

Day 14 clinical follow-up, CT scan

Follow-up Day 30- CT scan, NIH stroke scale, mRS

Timing of Evaluations

Registration- the start of the screening process when the study team is notified of a potentially eligible subject

Pre-Enrollment- all screening evaluations will be performed prior to enrollment

Enrollment- will occur prior to surgical intervention or receiving experimental medication

Medication period- Patients will continue on medication from immediately preoperatively to three days postoperatively or until discharge

Post Medication period- follow-up will continue until the patient is discharged from the neurosurgeon's care

Management of Adverse Events

All adverse events will be closely monitored and evaluated

Management of recurrent bleeding: recurrent SDHs will be managed according to best practices as determined by the treating physician

Criteria for Intervention Discontinuation

1. patient unable to tolerate side effects
2. thromboembolic complication including stroke, MI, DVT or PE
3. if in the investigator's judgment, withdrawal from the trial will be in the patients best interest
4. consent is withdrawn by the patient or their legal representative

End Points

1* Incidence of medication related complications including stroke, MI, DVT, or PE and other drug related adverse events

2- Return to OR for same sided surgery

2* Postop hematoma expansion, functional outcome (mRS, NIHSS) discharge location, LOS, volume of hematoma at 30 days

Tranexamic acid for cSDH – A Pilot Study on the Safety of Tranexamic Acid for the Chronic Subdural Hematoma Population

Data Points

Age, presenting symptom, admission GCS, language and motor function, preoperative living situation, width of hematoma, visible septations present, extent of MLS, operative approach, drain used, new preoperative deficit, immediate postop hematoma width, LOS, discharge GCS, language and motor function, discharge location, width of hematoma on follow up imaging, medication not tolerated, medication side effects, thromboembolic complications, other complications, blood loss, NIH stroke scale Day 0 and 30, mRS day 0 and 30

Statistical Data Analysis

Frequencies will be reported for ordinal and categorical variables. Descriptive analyses of central tendency (mean) will be used for continuous variables. Nonparametric tests will be used for statistical comparison, including the Kruskal-Wallis rank-sum test for multiple groups and the Mann-Whitney U test for 2 groups. Data tabulation and analysis will be analyzed using R statistical software version 3.4.2 (R Foundation for Statistical Computing, Vienna, Austria). Chi-square test, analysis of variance (ANOVA), and multivariate linear and log-linear regression models where appropriate. A P value < 0.05 will be considered statistically significant. P values for difference among time point means (preoperative, postoperative days 3, 7 and 30) to be determined by ANOVA.

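### A single-arm pilot of 50 can estimate complication rates but cannot establish safety, and the plan gives the 1* safety endpoint no interval

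*Combined protocol and SAP*

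**What the plan says.** Objective 1, under Study Objectives, is to "Establish the safety of using tranexamic acid in the treatment of chronic subdural hematomas". Study Design describes a "single center single armed study of 50 patients to determine the safety of tranexamic acid" and adds: "This will be compared to historical controls". No source, number or event rate is given for those controls. The same section gives the purpose: "This study intends to be a prerequisite to a large nationally funded randomized control trial".

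Under End Points, the item marked 1* is "Incidence of medication related complications including stroke, MI, DVT, or PE and other drug related adverse events". Study Interventions states: "All patients will have clinical follow-up on Day 30 +/- 7 days". Timing of Evaluations continues follow-up beyond that, until the neurosurgeon discharges the patient from care.

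The Statistical Data Analysis section is general. Its provision for a categorical endpoint is "Frequencies will be reported for ordinal and categorical variables". It also lists rank tests, chi-square, ANOVA and regression models, with significance at P < 0.05, but links none of them to the 1* endpoint. The only analysis tied to particular time points is an ANOVA of means. The documents contain no confidence interval, acceptable event rate, precision target or derivation of the 50.

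**The concern.** *Establish* and *determine* are confirmatory verbs. To meet an objective worded that way, a plan needs either a rate that would count as safe or a comparison able to rule out harm. This plan has neither, so no result is defined as meeting or failing Objective 1.

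The planned output for the main safety endpoint is a frequency. If no thromboembolic events occur, that output is 0%, and nothing beside it shows how high the true rate could still be. This matters because the study is intended to lead to a randomised trial, so whatever it reports about safety will be carried forward. The protocol's Supporting Data section shows how readily a small series is read in this way: it says that one "showed the safety and potential efficacy of treating chronic subdural hematomas in their retrospective study of 21 patients". An interval printed next to the count would guard against the same reading of these 50 patients.

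**Working it through.** **The plan's own figure.** The only sample-size figure is N = 50, in Study Design. It cannot be reproduced or refuted, because no event rate, margin, precision target, power or dropout allowance is given.

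**Inputs.** N = 50 comes from Study Design. The two-sided 95% level is a convention adopted here: the plan states P < 0.05 but no confidence level or sidedness. The event counts, true rates and reduced numbers followed (45 and 40) are assumptions.

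**Step 1. Upper limit when no event of a type is seen.** The exact (Clopper-Pearson) two-sided 95% upper limit for 0/n is 1 − 0.025^(1/n).

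- n = 50: 1 − 0.025^(1/50) = 0.0711, or 7.1%
- n = 45: 1 − 0.025^(1/45) = 0.0787, or 7.9%
- n = 40: 1 − 0.025^(1/40) = 0.0881, or 8.8%

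For n = 50 the one-sided 95% limit is 1 − 0.05^(1/50) = 0.0582, or 5.8%. The Wilson two-sided limit is 7.13% and the rule of three gives 3/50 = 6.0%. The choice of method does not alter the conclusion.

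**Step 2. Other counts in 50** (exact two-sided 95%; the lower limit is the 0.025 quantile of Beta(x, 51 − x) and the upper limit the 0.975 quantile of Beta(x + 1, 50 − x)).

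| Events | Observed | 95% interval |
|---|---|---|
| 1 | 2% | 0.05% to 10.65% |
| 2 | 4% | 0.49% to 13.71% |
| 5 | 10% | 3.33% to 21.81% |
| 10 | 20% | 10.03% to 33.72% |

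The zero-event case suits a single component such as stroke or PE. The whole 1* endpoint also includes other drug-related adverse events, so a non-zero count is more plausible there. The lower rows show that it too would be imprecise.

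**Step 3. How often zero events would be seen although the risk is real.** The chance of no event in 50 is (1 − p)^50.

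- p = 1%: 0.99^50 = 0.605
- p = 2%: 0.98^50 = 0.364
- p = 3%: 0.97^50 = 0.218
- p = 5%: 0.95^50 = 0.077

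At an assumed true rate of 2% for one type of event, the study would show none of them about 36% of the time.

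**The case against.** The strongest reply is that the documents already limit the claim. The title calls this a pilot, Study Design places it ahead of a randomised trial, and the 1* endpoint is itself worded as an incidence. Frequencies are planned, they cover that incidence, and a reader given the count could derive the limit. On this view only two verbs are at fault.

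Much of that stands. The choice of a pilot design is not in question, and it would be wrong to say that the plan has no method at all for the endpoint. What remains is that Objective 1 is still worded as a confirmatory claim, and that the quantity which would keep a reader from over-interpreting a low count is left for the reader to work out.

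Three stronger readings are tempting and are not supported.

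- *Fifty patients are too few.* Whether 7.1% is too high depends on an acceptable rate, and the documents give none.
- *The plan would declare the drug safe.* No section states a conclusion or decision rule. The criterion is undefined, which is a different fault.
- *The safety background rests on the 21-patient series.* Supporting Data also cites randomised trials without increased thromboembolic risk and a gynaecological study of over 3000 patients without thromboembolic complications. Those populations differ from this one, so they do not settle Objective 1, but the case does not rest on 21 patients.

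**Conclusion.** The point holds as one of wording and of a missing interval. Objective 1 and the matching phrase in Study Design promise more than a single arm of 50 can deliver, and for the 1* endpoint the plan supplies generic frequencies only. Zero events of a type would leave rates of up to 7.1% compatible with the data, or 7.9% and 8.8% if only 45 or 40 patients were followed to Day 30.

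These limits rest on the two-sided 95% convention, on independent patients, and on complete ascertainment of events in those counted. The true rates used for the zero-event probabilities are illustrations, not figures from the documents. A reader might go on to infer that the sample size is wrong. With no acceptable rate stated, the documents show only that it is not justified.

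**What to change.** 1. Reword Objective 1 as: *Estimate the incidence of stroke, MI, DVT, PE and other drug related adverse events in patients given tranexamic acid.* In Study Design, change only the phrase about determining safety to *to estimate the incidence of complications*. Keep the statement of one centre, one arm and 50 patients.
2. In the Statistical Data Analysis, make the primary analysis the count, proportion and two-sided 95% Clopper-Pearson interval for the whole 1* endpoint and for each of stroke, MI, DVT and PE. Use patients who received at least one dose, from first dose through the Day 30 (± 7 days) visit. Count stroke, MI, DVT and PE regardless of judged attribution, because without a concurrent control arm attribution is a matter of judgement. Count other adverse events when judged drug-related.
3. Report how many patients lacked the Day 30 visit. The primary analysis counts them as event-free unless an event was recorded, so repeat the interval in patients followed to Day 30 or with an earlier event. List events after that visit separately, since Timing of Evaluations continues follow-up beyond it.
4. State the precision in the plan: zero events of a type excludes rates above 7.1% with 50 patients followed to Day 30, 7.9% with 45 and 8.8% with 40 (two-sided 95%).
5. Describe any safety comparison with historical controls as descriptive only.

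The cost is two rewordings and a short addition to the analysis section, with no extra patients. The stated claim becomes less favourable. Events after the Day 30 visit fall outside the primary count. Counting thromboembolic events regardless of attribution may raise it. The separate intervals are each 95%, not jointly 95%.

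### The plan does not apply the trial's anticoagulation and clotting exclusions to the historical controls, and anticoagulant use is not a listed Data Point, so the return-to-OR comparison could neither show nor adjust for a difference in anticoagulation.

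*Combined protocol and SAP*

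**What the plan says.** All references are to the combined protocol and SAP.

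- **Study Objectives**, item 2: "Determine if the use of oral tranexamic acid reduces the rate of ipsilateral recurrence following drainage of chronic subdural hematomas". The matching item under End Points is "Return to OR for same sided surgery".
- **Study Design**: one arm, 50 patients, and "This will be compared to historical controls". The source, period, number and eligibility of the controls are not given. Statistical Data Analysis does not mention them.
- **Exclusion Criteria**: these remove "patients requiring long-term anticoagulation- unable to stay off for less than 30 days", which I read as patients whose anticoagulant cannot be held. They also remove "history of thromboembolic problem including stroke, MI, DVT, PE", irreversible coagulopathy and known clotting disorder. They stand under subject selection, and nothing extends them to the controls.
- **Prohibited Interventions**: "Therapeutic anticoagulation".
- **Study Interventions**, on DVT prevention: "Pharmacologic prophylaxis will be at the discretion of the treating physician".
- **Criteria for Intervention Discontinuation**: study drug stops after "thromboembolic complication including stroke, MI, DVT or PE".
- **Data Points**: a specific list that includes septations, midline shift, drain use and blood loss. It has no item for anticoagulants, coagulation status or past thromboembolism. Thromboembolic complications appear, but as an outcome.
- **Statistical Data Analysis**: regression models are to be used where appropriate, with no covariates named, and the significance threshold is P < 0.05.

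**The concern.** The protocol selects its own patients on anticoagulation and clotting status. Unless the controls are selected in the same way, the design can itself create a difference between the groups. The Background attributes recurrence to continued bleeding into the hematoma cavity, so anticoagulation is a plausible risk factor for reoperation, although the documents do not say that it is one.

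Trial exposure need not be zero either. A patient whose anticoagulant can be held may enrol, prophylaxis is discretionary, and a patient who has a thromboembolic event may later be treated. None of this would appear in the listed data, so a regression limited to those data has no variable for it.

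With one arm, only the controls can answer the second objective. If more controls than trial patients were anticoagulated, and anticoagulation raises reoperation, the drug would look better than it is. The study is described as a prerequisite to a large randomized trial, so a spurious recurrence signal could mislead that trial's planning.

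**Working it through.** The plan has no figure to reproduce here: it gives no basis for the 50 patients, and no control rate or number of controls. The calculation below shows only how large the effect could be.

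**Inputs.** From the documents: n = 50, the P < 0.05 threshold, and 33%, which the Background gives as the upper end of reported recurrence. Assumed: 33% or 20% as the control rate r; share of controls exposed, c, 10% to 30%; share of trial patients exposed, t, 0% to 20%; risk ratio RR for reoperation, 1 to 2; 150 controls; a two-sided test.

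**Formula.** If unexposed patients have rate p0, a group with exposed share e has rate p0(1 + e(RR − 1)). With no drug effect, the trial rate is therefore

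r × (1 + t(RR − 1)) / (1 + c(RR − 1)).

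For t = 0, c = 30%, RR = 2 this is 20% × 1/1.3 = 15.4%, which is 4.6 points lower, and 33% × 1/1.3 = 25.4%, which is 7.6 points lower.

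**Chance of P < 0.05 favouring the drug.** This comes from exact enumeration of both binomial counts, 50 against 150, using the chi-square test. The plan does not say whether the test is continuity-corrected, so the table gives both results (uncorrected / corrected).

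| t, c, RR | Trial rate, r = 20% | Chance | Trial rate, r = 33% | Chance |
|---|---|---|---|---|
| t = c, or RR = 1 | 20.0% | 2.1 / 1.2% | 33.0% | 2.4 / 1.5% |
| 0, 10%, 1.5 | 19.0% | 2.9 / 1.7% | 31.4% | 3.7 / 2.4% |
| 0, 20%, 2 | 16.7% | 6.1 / 3.8% | 27.5% | 10.2 / 7.1% |
| 10%, 30%, 2 | 16.9% | 5.7 / 3.5% | 27.9% | 9.2 / 6.3% |
| 0, 30%, 2 | 15.4% | 9.0 / 5.8% | 25.4% | 16.2 / 11.8% |
| 20%, 10%, 2 | 21.8% | below first row | 36.0% | below first row |

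The last row is the reversed case: 1.8 and 3.0 points against the drug.

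**Number of controls.** With 100, 150, 200, 250 or 300 controls, the top case (0, 30%, 2) gives 9.0% to 9.6% uncorrected and 5.5% to 6.2% corrected at r = 20%. At r = 33% it gives 15.4% to 17.5% and 11.1% to 13.4%.

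**Precision of the trial arm.** The 95% half-width is 1.96 × √(r(1 − r)/50): 11.1 points at 20% and 13.0 points at 33%. Every shift above is smaller.

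**Why controls should not be dropped for later anticoagulation.** An anticoagulant may be started after surgery because no recurrence has occurred. In the worst case, where all dropped controls are recurrence-free, dropping 10% to 20% of them raises a 20% rate to 20/0.9 = 22.2% or 20/0.8 = 25.0%. A 33% rate rises to 33/0.9 = 36.7% or 33/0.8 = 41.3%. The repair would then create a bias of its own in favour of the drug.

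**The case against.** **The harm is assumed.** No section says that anticoagulation raises reoperation, how common it is, or who the controls are. With RR = 1 or equal exposure nothing remains. This stands: the documents show an omission, not a bias. A reader might infer that the comparison will favour tranexamic acid, but the text does not support that.

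**The effect is small beside the noise.** This also stands, and the 16.2% figure needs every assumption at its least favourable value, including zero trial exposure. But a systematic shift does not average out, and here the listed data could not reveal it.

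**Anticoagulant status is not really unknown.** Pre-enrollment screening must check the exclusions, so the team will learn a trial patient's preoperative status. The Data Points list is not declared exhaustive, and it does not name return to OR either. A reader might infer that exposure is unknowable in the trial arm. The supportable statement is narrower: it is not listed for recording or analysis.

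**This is a safety pilot.** The sentence on historical controls follows a sentence about safety, no return-to-OR test against controls is specified, and a randomized trial would remove this confounding. That lowers the severity. It does not remove the recurrence objective, which cannot be answered without a comparator. The thromboembolic-history exclusion could also affect a safety comparison with the same controls; that is not sized here.

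**Anticoagulation is one covariate of a wider gap.** The controls are undefined in every respect. Anticoagulation is singled out because the trial's own exclusions select on it and the Data Points omit it.

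**Conclusion.** The point holds in limited form. If the plan is followed as written, the return-to-OR comparison with historical controls could neither show nor adjust for a difference in anticoagulation, a difference that the trial's own exclusions can create.

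Size and direction are not established. With the assumed exposures and risk ratios, trial exposure no higher than control exposure, and 150 controls, the chance of a falsely favourable result rises from about 2% to at most 9% (20% control rate) or 16% (33%) uncorrected, and to at most 6% or 12% corrected. The direction reverses if trial patients are the more exposed group.

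This is a cheap improvement of low to moderate severity. It is not evidence that the recurrence result will be wrong.

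**What to change.** 1. Select historical controls with those inclusion and exclusion criteria that can be read from the chart, judged on status known at surgery. Do not drop a control because an anticoagulant was started after surgery.
2. Add to the Data Points, for both groups, anticoagulant use before surgery, and any postoperative anticoagulant (prophylactic or therapeutic) with its start date.
3. Stratify or adjust the return-to-OR comparison by preoperative anticoagulant use. Describe postoperative use in both groups without excluding or adjusting on it.
4. If controls cannot be screened this way, report the trial's return-to-OR rate with its 95% interval and give no P value against controls.

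**Cost.** One control eligibility rule, the added case report form fields, and chart abstraction of eligibility and anticoagulant use for each control. How much abstraction depends on the number of controls, which the plan does not give. Fewer controls may qualify. Nothing changes for the 50 patients or their treatment.

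### The anticoagulation exclusion is worded in reverse: read literally, it does not exclude patients who can stop only briefly and must restart before 30 days

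*Combined protocol and SAP*

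**What the plan says.** The combined protocol and SAP deals with anticoagulation in a few short lines.

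- **Exclusion Criteria:** the only line with a time limit is "patients requiring long-term anticoagulation- unable to stay off for less than 30 days".
- **Prohibited Interventions:** the whole entry is "Therapeutic anticoagulation", with no period and no exception.
- **Overlapping exclusions:** the same list also removes "history of thromboembolic problem including stroke, MI, DVT, PE", "known clotting disorder" and "any patient not judged suitable for the study by the investigators".
- **Study Interventions:** "All patients will have follow-up CTs on postop days 1, 3, 7 and 30 +/- 7 days"; clinical follow-up has the same Day 30 window. On DVT prevention, "Pharmacologic prophylaxis will be at the discretion of the treating physician".
- **Criteria for Intervention Discontinuation:** study drug stops on a "thromboembolic complication including stroke, MI, DVT or PE".
- **End Points:** medication-related complications, thromboembolic events among them, come first. Same-side reoperation follows, then hematoma expansion and hematoma volume at 30 days.

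The Data Points section has no item for restarting an anticoagulant.

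**The concern.** A 30-day threshold in an anticoagulation exclusion makes sense as a minimum time off treatment. The line as written sets no minimum. It asks whether the patient is unable to manage an interruption shorter than 30 days, and almost anyone who can stop for surgery can manage that.

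The threshold bears on what the study measures. Restarting a therapeutic anticoagulant during follow-up can affect both thromboembolic events, in the first-listed endpoint, and rebleeding, which drives same-side reoperation and late hematoma volume. The study has one arm of 50 patients and is compared with historical controls, so no concurrent group is available to help interpret an event in such a patient. There is also a safety side. A patient who enters and must restart at Day 10 either breaks the prohibition, if it covers follow-up, or goes without needed treatment.

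**Working it through.** The plan gives no figure to reproduce, so the check is one of logic.

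**Inputs.** The exclusion wording and the Day 30 +/- 7 windows (Exclusion Criteria; Study Interventions); the unqualified prohibition (Prohibited Interventions); hematoma volume at 30 days (End Points). Let T be the longest time, in days, that a patient on long-term anticoagulation can stay off it.

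**Rules compared.**

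- Literal rule, taking the words after the dash as a condition: exclude if the patient cannot stay off for any period shorter than 30 days. This is true only when T = 0.
- Evident rule: exclude if T < 30.

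| T (days) | Literal rule | Evident rule |
|---|---|---|
| 0 | excluded | excluded |
| 7 | not excluded | excluded |
| 14 | not excluded | excluded |
| 29 | not excluded | excluded |
| 30 or more | not excluded | not excluded |

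The two rules disagree for every T above 0 and below 30. They agree only for patients who cannot stop at all and for those who can stay off for the full period.

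**Why the second rule is the evident one.** Under the literal rule the number 30 does almost no work. As a minimum, it matches the 30-day visit, the 30-day CT and the 30-day volume endpoint, and it fits a protocol that prohibits therapeutic anticoagulation.

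**Does other text supply the threshold?**

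- The prohibition governs treatment, not entry, and states no period.
- The exclusions for thromboembolic history and clotting disorder remove some candidates, but not a patient anticoagulated for another reason with no prior event.
- Investigator judgement permits exclusion but does not require it, and says nothing on time off treatment.

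None of them sets or corrects a 30-day limit.

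**Follow-up window.** The last scheduled CT and visit may fall from Day 30 - 7 = 23 to Day 30 + 7 = 37. A patient eligible under the corrected rule could therefore restart on Days 31 to 37, before a late scan, if the prohibition were taken to end at Day 30.

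**Start of the clock.** The criterion does not say whether the 30 days run from stopping the drug or from surgery.

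**The case against.** The strongest reply is that the line is garbled rather than plainly reversed. It is two fragments joined by a dash. The first can stand alone as the exclusion, with the second as a clumsy gloss; the patient who must restart at Day 10 is then excluded. This stands to the extent that the literal reading above is the most natural one, not the only one. It does not rescue the text: if the first fragment stands alone, patients with T of 30 or more are excluded too and the 30-day clause has no function. If the gloss is read sensibly, the reader has silently corrected it.

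It is also fair that misapplication is unlikely. The literal rule would exclude almost nobody, since every participant has operative drainage and therapeutic anticoagulation is prohibited. This is one center, and its staff would probably see what was meant. The overlapping exclusions and investigator judgement contain much of the remaining risk. All of this lowers the likely impact but leaves the written rule wrong.

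A reader might infer more in three ways, none of them supported:

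- That unsuitable patients were or will be enrolled. The documents show a wording error, not enrollment under it.
- That the span of T where the two rules differ measures the size of the problem. It counts days of tolerance, not patients, events or bias.
- That the missing restart field is part of the same error. It does not follow from the reversed wording; recording a restart is a useful option only.

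**Conclusion.** The point holds as a correction to an operative eligibility rule. On its most natural literal reading, the criterion fails to exclude patients who can stop anticoagulation only briefly and must restart before 30 days, and nothing else in the document states the intended threshold.

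The size cannot be estimated. The documents give no share of candidates on long-term anticoagulation and no distribution of how long they could stay off it. The affected group is probably small. The direction of any net effect on the endpoints is unknown, so the wording is no ground for saying that the results would be biased one way.

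The conclusion rests on one inference, that the 30 days are meant as a minimum time off treatment. The prohibition and the 30-day assessments support it strongly. The correction is still worth making: the rule concerns safety, the change costs almost nothing, and the study is meant to lead to a large randomized trial into which the wording could be carried.

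**What to change.** Reword the exclusion to: *patients requiring long-term anticoagulation who are unable to stay off it for at least 30 days after surgery*. The investigators should confirm that the 30 days start at surgery, since the present text does not say.

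Leave the prohibition on therapeutic anticoagulation unshortened. It is now unqualified, and ending it at Day 30 could narrow it while the last scheduled visit and CT may still be a week away. If a period is stated, it should run through that visit and CT, up to Day 37, with an exception for treating a new thromboembolic event. Pharmacologic DVT prophylaxis can stay at the treating physician's discretion, as now.

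Optionally, record the date of any anticoagulant restart, which would help in judging whether an individual event is related to study drug. It would not by itself make the historical comparison fair.

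The cost is one reworded line and, if wanted, one sentence on the prohibition and one data item. No visits or tests are added. Candidates who cannot stay off for 30 days would be screened out, as the rule evidently intends.
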